2.4 Pediatric Studies

2.4.1 Prior Experience in Children

Tipifarnib has been well tolerated in pediatric patients, but the activity of tipifarnib in pediatric malignancies to date has been disappointing. 40-42,45,46 For example, in a phase I trial of tipifarnib in children with solid tumors or neurofibromatosis type 1 (NF1)-associated plexiform neurofibromas, the maximum tolerated dose (MTD) was determined to be 200 mg/m²/dose given twice daily for 21 days, repeated every 28 days. 41 The observed dose limiting toxicities (DLT) in Cycle 1 were myelosuppression, rash, nausea, vomiting and diarrhea, and no cumulative toxicities were observed. Although the farnesyltransferase activity at the MTD, determined by the percent HDJ2 prenylation in peripheral blood mononuclear cells (PBMCs) was 30% of baseline, no objective responses were observed. 41 Similarly, a phase I trial of tipifarnib in children with leukemia, used a dose of 300 mg/m2/dose given twice daily for 21 days, repeated every 28 days, with observed DLTs of rash, mucositis, and nausea, vomiting and diarrhea. Importantly, neurotoxicity, which was dose limiting in adult patients, was not observed in pediatric patients treated with tipifarnib. 40 Again, although farnesyltransferase activity was inhibited in leukemic blasts, no objective responses to tipifarnib

treatment were observed in this study. Tipifarnib also failed to show clinical benefit in phase II studies in pediatric patients with diffuse intrinsic pontine glioma (DIPG), juvenile myelomonocytic leukemia (JMML) or NF1-associated plexiform neurofibromas. ^{42,45,46}

The lack of response to tipifarnib in pediatric malignancies may have been, in part, because these trials were conducted without genomic pre-selection of treatment subjects to include only patients with somatic *HRAS* mutations. The study in patients with JMML was the only study of tipifarnib in pediatric patients to identify somatic driver mutations in enrolled patients, but *HRAS* mutations were not among the panel of genes tested. Recently, promising activity of tipifarnib has been demonstrated in adult patients with HRAS-driven head and neck squamous cell carcinoma (HNSCC). ⁵² Tipifarnib may be similarly effective in pediatric patients with mutant HRAS-driven tumors.

2.4.2 Pharmacology/Pharmacokinetics/Correlative Biological Studies

As noted above, pharmacodynamic measurement of tipifarnib activity in the context of pediatric trials was measured by evaluating the percent farnesylation of HDJ2, in either peripheral blood mononuclear cells or leukemic blasts.

however, the pharmacokinetics of tipifarnib given in a one week on, one week off dosing schedule has not yet been evaluated in children.²⁶

2.5 Overview of Proposed Pediatric Study

This is a phase 2 trial of tipifarnib in children with recurrent or refractory solid tumors, CNS tumors, non-Hodgkin lymphomas and histiocytic disorders harboring specific activating mutations in HRAS.

Doses of up to 300mg/m²/dose twice daily for 21 out of 28 days have been previously tolerated in children. This is equal to a total dose of 12,600mg/m² per cycle. Although the MTD in adults for the 7 day on/ 7 day off schedule was not determined, the current RP2D for adults is 600mg/dose twice daily on a 7 day on/ 7 day off schedule (total dose of 16,800 mg/ cycle; equal to ~9,700mg/m²/cycle, and therefore less than the cumulative cycle doses previously deemed safe in children). The pediatric dose of the current adult RP2D is mg/m²/dose twice daily mg/m²/cycle) and therefore, also less than doses previously deemed safe in children, and therefore will serve as the recommended dose for the pediatric MATCH trial.

Tipifarnib will be administered at mg/m²/dose by mouth twice daily for 7 days on followed by 7 days off alternating on a 28 day cycle (i.e., days 1-7 and 15-21 of a 28 day cycle).

The primary aim of this trial will be to establish the objective response rate to tipifarnib. While there will not be multiple pre-determined mutation-based cohorts, responses will be analyzed retrospectively with respect to specific HRAS mutations and variant allele frequency.

Key secondary objectives include further evaluation of the tolerability of tipifarnib in pediatric patients. Toxicity will be assessed using CTCAE V5.0. Imaging for disease evaluation will occur every other cycle x 3, then every three cycles. Disease response will

be assessed according to RECIST v1.1 for solid tumors and 2-dimensional measurement for CNS tumors.

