The effect of intermittent schedules of tipifarnib was tested in several adult phase 1 studies, including a 5-day bid dosing followed by 9-day rest (5-day schedule)⁴⁹ and two trials investigating a 7-day bid dosing followed by 7-day rest (7-day schedule).^{50,51} In the 5-day schedule phase 1 trial in patients with non-hematological malignancies, doses from 25 to 1300 mg bid were explored. No MTD was identified. Dose-limiting toxicity of grade 3 neuropathy was observed in one patient and grade 2 fatigue in 4 of 6 patients treated with 1300 mg bid. Fatigue that was not dose-limiting was observed at the prior dose level (800 mg bid). Of note, myelosuppression which was the most common toxicity in the 21-day schedule, was limited with the 5-day schedule and included a grade 3 neutropenia in a patient with a prior history of myelosuppression treated with 50 mg bid and a grade 2 thrombocytopenia in a patient treated at the 1300 mg bid dose level. No objective responses were noted. ²⁶

In the first of the weekly schedule studies,⁵⁰ the starting dose was 300 mg bid with 300 mg dose escalations to a maximum planned dose of 1800 mg bid. Two of 6 patients with non-hematological tumors in dose level 3 (900 mg bid) developed grade 3 fatigue attributable to study drug, and 600 mg bid on alternate weeks was identified as the recommended phase 2 dose. There were no objective responses but 4 out of 21 patients, 3 of whom had NSCLC, remained on study for at least 1 year with stable disease (12, 13, 16 and 17 months). Five grade 3 events of myelosuppression (out of 21 patients) were described by the authors (doses not indicated) that were not considered dose limiting toxicities (DLTs) and hematological toxicity was described as moderate and manageable. ²⁶

The second weekly schedule study was conducted in patients with relapsed/refractory AML.⁵¹ Tipifarnib was administered bid on days 1–7 and days 15–21 of 28-day cycles at doses up to 1600 mg bid. At the 400 mg bid dose level, a grade 5 hepatorenal failure occurred, potentially related to the study drug. There

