were no additional DLTs reported at 600, 800 or 1000 mg bid dose levels. At the 1200 mg bid dose level, a Grade 3 creatinine elevation was seen in one patient out of 6 treated. At the 1400 mg bid dose level, one patient experienced a Grade 4 hypotension and a rising Grade 2 creatinine that were dose limiting, and a second patient had a rising Grade 2 creatinine that resulted in treatment discontinuation and was therefore considered dose limiting. At the 1600 mg dose level, Grade 3 liver function tests and a rising Grade 2 creatinine were dose limiting, and in a second patient, a rapidly rising creatinine was seen and treatment stopped. As a result, the 1200 mg bid dose was established as the MTD and 7 additional patients treated. Sixteen patients were treated at the 1000 and 1200 mg dosing levels, with 3 of them experiencing complete responses. No formal responses were seen among patients treated at the lower dose levels.²⁶

The tipifarnib regimen investigated in KO-TIP-001, a phase 2 study of tipifarnib in nonhematological malignancies that carry HRAS mutations was set with a starting dose of 900 mg, orally, bid on days 1-7 and 15-21 of 28-day treatment cycles. Preliminary data from KO-TIP-001 indicate a tolerability that is broadly similar to the safety profile observed of other tipifarnib regimens in prior clinical studies which administered tipifarnib daily in a 21-day on, 7 days off treatment cycle schedule. The most common AES of tipifarnib including hematological events, gastrointestinal disturbances (nausea, vomiting and diarrhea) and fatigue have been monitorable and manageable with protocol defined assessments and management of toxicity guidance.

and several subjects have maintained their response and continued on treatment . 26

Based on these data, the starting dose for the tipifarnib alternative week regimen was mg, orally, bid on days 1-7 and 15-21 of 28-day treatment cycles. Stepwise to control treatment-related, treatment-emergent toxicities are allowed and specific toxicity management is detailed in each clinical study protocol.²⁶

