APPENDIX V: TIPIFARNIB DOSING NOMOGRAM

Tipifarnib Dose Assignment: 350 mg/m² PO BID (maximum dose: 600 mg PO BID)

BSA (m2)	Tipifarnib Dosing	Total Daily Dose (mg/day)	Dose Reduction
0.29-0.35	100 mg PO BID	200 mg	Off-study
0.36-0.5	200 mg PO AM 100 mg PO PM	300 mg	100 mg PO BID
0.51-0.64	200 mg PO BID	400 mg	200 mg PO AM 100 mg PO PM
0.65-0.78	300 mg PO AM 200 mg PO PM	500 mg	200 mg PO AM 100 mg PO PM
0.79-0.93	$300~\mathrm{mg}~\mathrm{PO}~\mathrm{BID}$	600 mg	200 mg PO BID
0.94-1.07	400 mg PO AM 300 mg PO PM	700 mg	300 mg PO AM 200 mg PO PM
1.08-1.21	400 mg PO BID	800 mg	300 mg PO BID
1.22-1.36	500 mg PO AM 400 mg PO PM	900 mg	300 mg PO BID
1.37-1.5	500 mg PO BID	1000 mg	400 mg PO AM 300 mg PO PM
1.51-1.64	600 mg PO AM 500 mg PO PM	1100 mg	400 mg PO BID
≥1.65	600 mg PO BID	1200 mg	500 mg PO AM 400 mg PO PM

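### Does Section 2.5 wrongly call the pediatric dose lower than doses deemed safe in children, given the solid-tumor MTD in Section 2.4.1?

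*Combined protocol and SAP*

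**What the plan says.** Section 2.5 measures dose as cumulative mg/m² per 28-day cycle. It takes 300 mg/m² twice daily for 21 days as previously tolerated in children and gives the total as 12,600 mg/m². It then takes the adult recommended phase 2 dose on the week-on, week-off schedule, 600 mg twice daily (16,800 mg, or about 9,700 mg/m², per cycle), and calls it "and therefore less than the cumulative cycle doses previously deemed safe in children". The pediatric version of that dose is described as "also less than doses previously deemed safe in children, and therefore will serve as the recommended dose" for this trial. Its value is blacked out in Section 2.5, but Appendix V states it: "Tipifarnib Dose Assignment: 350 mg/m² PO BID (maximum dose: 600 mg PO BID".

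Section 2.4.1 describes two pediatric phase 1 results. In children with solid tumors or NF1 plexiform neurofibromas, "the maximum tolerated dose (MTD) was determined to be 200 mg/m²/dose given twice daily for 21 days" of each 28-day cycle. The other is "a phase I trial of tipifarnib in children with leukemia, used a dose of 300 mg/m2/dose given twice daily for 21 days", also in 28-day cycles. Dose-limiting toxicities were seen in both trials.

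On adult data, Section 2.5 opens a sentence with "Although the MTD in adults for the 7 day on/ 7 day off schedule was not determined". Section 2.3.3.2 reports two adult trials of that schedule. In non-hematological tumors, after grade 3 fatigue in 2 of 6 patients at 900 mg twice daily, "600 mg bid on alternate weeks was identified as the recommended phase 2 dose". In AML, "the 1200 mg bid dose was established as the MTD".

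**The concern.** A reader who sets Section 2.5 beside Section 2.4.1 finds that the safety comparison uses the higher of two pediatric results and leaves out the lower. The omitted result is the one labelled an MTD. It also comes from the population closer to this trial, which enrolls solid tumors, CNS tumors, non-Hodgkin lymphomas and histiocytic disorders but not leukemia. On the protocol's own yardstick, the planned dose lies above that MTD.

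The adult sentence adds to the doubt. It says without qualification that no MTD was determined on this schedule, yet one is reported for AML two sections earlier.

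If the rationale were wrong in substance, children could be treated on a safety margin that does not exist. Section 2.4.2 makes the question more pointed, because it says that pharmacokinetics on the week-on, week-off schedule have not been studied in children. (Text just before that statement is missing from the public copy.)

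**Working it through.** **Inputs.** Section 2.5: 300 mg/m² twice daily × 21 days; adult 600 mg twice daily × 14 days. Section 2.4.1: 200 mg/m² twice daily × 21 days. Appendix V: 350 mg/m² twice daily, maximum 600 mg per dose. Section 5.1: dosing on Days 1–7 and 15–21, so 14 days per cycle. Section 2.3.3.1: usual adult 21-day dose, 300 mg twice daily.

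**Formula.** Cycle total = dose × 2 per day × dosing days.

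1. *The plan's own figures.* 300 × 2 × 21 = 12,600 mg/m², as printed. 600 × 2 × 14 = 16,800 mg, as printed. Assuming a body surface area (BSA) of 1.73 m², 16,800 / 1.73 = 9,711, which matches the printed 9,700 or so. Section 2.5 does not state the BSA it used; 1.70 to 1.80 m² gives 9,882 to 9,333.

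2. *The omitted comparator.* 200 × 2 × 21 = 8,400 mg/m².

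3. *The planned dose.* 350 × 2 × 14 = 9,800 mg/m².
   - Against 12,600: 9,800 / 12,600 = 0.778, which is 22% lower.
   - Against 8,400: 9,800 / 8,400 = 1.167, which is 17% higher.
   - Adult equivalent against 8,400: 9,711 / 8,400 = 1.156, about 16% higher.

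4. *Delivered dose under Appendix V* (daily mg × 14 / BSA). Tablet rounding moves the total within each band. The lowest value below 2.0 m² is 200 × 14 / 0.35 = 8,000, and the highest is 300 × 14 / 0.36 = 11,667. At 2.0 m² the cap gives 16,800 / 2.0 = 8,400, and larger patients receive less per m². No band reaches 12,600. Most patients below 2.0 m² would therefore fall between the two pediatric totals, as the nominal figure does.

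5. *Does a cycle total carry over from one schedule to another?* The adult figures in the protocol allow a check. The usual 21-day regimen is 300 × 2 × 21 = 12,600 mg per cycle, and the alternate-week recommended dose is 16,800 mg. The ratio is 16,800 / 12,600 = 1.33. In adults, the recommended alternate-week total is thus a third above the usual 21-day total. Exceeding a 21-day MTD by 17% on a 14-day schedule does not in itself show that tolerance is exceeded.

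6. *Where the dose number comes from.* 600 / 1.73 = 347 mg/m², close to 350. Section 11.2.1 gives the general Pediatric MATCH approach: where the adult recommended dose is below the adult MTD, it is normalized to body size and used, with later optimization expected. Section 2.5 likewise calls the trial dose the pediatric form of the adult recommended dose. The pediatric comparison reads as a supporting check, not as the source of the number.

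7. *The adult-MTD sentence.* It goes on to the 600 mg dose, which Section 2.3.3.2 takes from the trial in non-hematological tumors, where no MTD is named. The 1200 mg MTD belongs to AML. Read for solid tumors, the sentence agrees with Section 2.3.3.2; what it lacks is the population.

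**The case for a change.** The strongest reply is that schedule cannot be used to set aside one comparator only. Both pediatric trials dosed on 21 of 28 days. If the difference in schedule disqualifies 8,400, it also disqualifies 12,600, and the printed argument loses its support. Section 2.5 does not argue that intermittent dosing is better tolerated, although Section 2.3.3.2 offers some adult evidence for it. Per dosing day, the planned 700 mg/m² (350 × 2) is above both earlier trials (400 and 600). And Section 2.5 uses the word therefore, so it does rest the choice of dose on the comparison.

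Most of this stands as criticism of the prose: the comparison is weak evidence in either direction, and a fuller paragraph would show both results. Section 11.2.1 is also not a perfect answer, since its heading refers to agents without pediatric phase 1 data.

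What does not stand is the step from an incomplete rationale to a contradiction. Section 2.5 states the dose and schedule of its benchmark and is correct against it. Saying that doses up to 300 mg/m² were tolerated does not deny that another trial set a lower MTD, and that MTD is reported in full in Section 2.4.1.

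**Conclusion.** The observation is accurate: Section 2.5 cites one of two pediatric results, and the nominal 9,800 mg/m² per cycle lies between them, 22% below one and 17% above the other. The adult-MTD sentence lacks a population qualifier. Neither point calls for a change to the plan. Both concern background text, and every figure printed there reproduces.

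Nothing operational depends on the comparison. Dosing follows Appendix V. Dose-limiting toxicity is defined in Section 5.4. Section 8.1 requires weekly clinical and laboratory checks in Cycle 1. Section 14.4 provides review by the data and safety monitoring committee and on a weekly leadership call. The primary decision rule in Section 11.3, at least 3 responses among 20 evaluable patients, makes no use of it. Adding the second comparator would leave treatment, data and conclusions as they are.

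This rests on three assumptions: that the value blacked out in Section 2.5 is the 350 mg/m² of Appendix V; that the 12,600 benchmark is the leukemia trial, the only pediatric experience at that dose described in Section 2.4.1; and, for the 9,711 and 347 figures, that BSA is 1.73 m². The calculation does not show that the dose is safe or unsafe, and no view is taken on which dose is right. Sections 2.3.3.2, 2.4.1 and 2.5 and Appendix V need to be read together. Reconciling their wording is an editorial matter for the clinical team when that text is next opened.

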3.0 SCREENING AND STUDY ENROLLMENT PROCEDURES

3.1 Study Enrollment

Patient enrollment for this study will be facilitated using the Oncology Patient Enrollment Network (OPEN), a web-based registration system available on a 24/7 basis. It is integrated with the NCI Cancer Trials Support Unit (CTSU) Enterprise System for regulatory and roster data and, upon enrollment, initializes the patient position in the RAVE database.

3.1.1 Access requirements for OPEN:

Patient enrollment will be facilitated using the Oncology Patient Enrollment Network (OPEN). The Oncology Patient Enrollment Network (OPEN) is a web-based registration system available on a 24/7 basis. OPEN is integrated with CTSU regulatory and roster data and with the Lead Protocol Organization (LPOs) registration/randomization systems or Theradex Interactive Web Response System (IWRS) for retrieval of patient registration/randomization assignment. OPEN will populate the patient enrollment data in NCI's clinical data management system, Medidata Rave.

Requirements for OPEN access:

- A valid CTEP-IAM account;
- To perform enrollments or request slot reservations: Be on a LPO roster, ETCTN
 Corresponding roster, or PO roster with the role of Registrar. Registrars must hold a
 minimum of an AP registration type;
- Have an approved site registration for a protocol prior to patient enrollment.

To assign an Investigator (IVR) or Non-Physician Investigator (NPIVR) as the treating, crediting, consenting, drug shipment (IVR only), or receiving investigator for a patient transfer in OPEN, the IVR or NPIVR must list the IRB number used on the site's IRB approval on their Form FDA 1572 in RCR.

Prior to accessing OPEN, site staff should verify the following:

- Patient has met all eligibility criteria within the protocol stated timeframes;
 and
- All patients have signed an appropriate consent form and HIPAA authorization form (if applicable).

Note: The OPEN system will provide the site with a printable confirmation of registration and treatment information. Please print this confirmation for your records.

Access OPEN at https://open.ctsu.org or from the OPEN link on the CTSU members' website. Further instructional information is in the OPEN section of the CTSU website at https://open.ctsu.org. For any additional questions, contact the CTSU Help Desk at [name] or ctsu.org. For any additional questions, contact the CTSU Help Desk at [name] or ctsu.org.

Please see		
10.0		

3.1.2 IRB Approval

Each investigator or group of investigators at a clinical site must obtain IRB approval for this protocol and submit IRB approval and supporting documentation to the CTSU Regulatory Office before they can be approved to enroll patients. For CTEP and Division of Cancer Prevention (DCP) studies open to the National Clinical Trials Network (NCTN) and NCI Community Oncology Research Program (NCORP) Research Bases after March 1, 2019, all U.S.-based sites must be members of the NCI Central Institutional Review Board (NCI CIRB). In addition, U.S.-based sites must accept the NCI CIRB review to activate new studies at the site after March 1, 2019. Local IRB review will continue to be accepted for studies that are not reviewed by the CIRB, or if the study was previously open at the site under the local IRB. International sites should continue to submit Research Ethics Board (REB) approval to the CTSU Regulatory Office following country-specific regulations.

Sites participating with the NCI CIRB must submit the Study Specific Worksheet for Local Context (SSW) to the CIRB using IRBManager to indicate their intent to open the study locally. The NCI CIRB's approval of the SSW is automatically communicated to the CTSU Regulatory Office, but sites are required to contact the CTSU Regulatory Office at [contact] to establish site preferences for applying NCI CIRB approvals across their Signatory Network. Site preferences can be set at the network or protocol level. Questions about establishing site preferences can be addressed to the CTSU Regulatory Office by email or calling [name].

Sites using their local IRB or REB, must submit their approval to the CTSU Regulatory Office using the Regulatory Submission Portal located in the Regulatory section of the CTSU website. Acceptable documentation of local IRB/REB approval includes:

- Local IRB documentation;
- IRB-signed CTSU IRB Certification Form; and/or
- Protocol of Human Subjects Assurance Identification/IRB Certification/Declaration of Exemption Form.

In addition, the Site-Protocol Principal Investigator (PI) (i.e. the investigator on the IRB/REB approval) must meet the following criteria in order for the processing of the IRB/REB approval record to be completed:

- Holds an active CTEP status;
- Rostered at the site on the IRB/REB approval (applies to US and Canadian sites only) and on at least one participating roster;
- If using NCI CIRB, rostered on the NCI CIRB Signatory record;
- Includes the IRB number of the IRB providing approval in the Form FDA 1572 in the RCR profile; and
- Holds the appropriate CTEP registration type for the protocol.

Additional Requirements

Additional requirements to obtain an approved site registration status include:

- An active Federal Wide Assurance (FWA) number;
- An active roster affiliation with the Lead Protocol Organization (LPO) or a Participating Organization (PO); and
- Compliance with all protocol-specific requirements (PSRs).

Institutions with patients waiting that are unable to use the Portal should alert the CTSU Regulatory Office immediately at [name] in order to receive further instruction and support. For general (non-regulatory) questions call the CTSU General Helpdesk at: [name].

Note: Sites participating on the NCI CIRB initiative and accepting CIRB approval for the study are not required to submit separate IRB approval documentation to the CTSU Regulatory Office for initial, continuing or amendment review.

Investigators and site staff will need to be registered with CTEP and have a valid and active Cancer Therapy Evaluation Program-Identity and Access Management (CTEP-IAM) account (check at < https://ctepcore.nci.nih.gov/iam/). This is the same account (user id and password) used for credentialing in the CTSU members' web site. To perform registrations in OPEN, the site user must have been assigned the 'Registrar' role on the relevant Group or CTSU roster. OPEN can be accessed at https://open.ctsu.org or from the OPEN tab on the CTSU members' side of the website at https://www.ctsu.org. Registrars must hold a minimum of an AP registration type.

